^a Target Day and LTE Study Day are based on LTE Study Day 1.

7.1.1.2.3 *Fluid (Plasma, CSF) and PET Imaging (Amyloid and Tau) Biomarker Data*

Analysis visit windows for the biomarker parameters are defined in a similar manner as those for the efficacy parameters (refer to Section 7.1.1.2.2). Biomarker data will be allocated to analysis visits corresponding to the analysis visit window intervals in which they fall in as specified in **Error! Reference source not found.** to **Error! Reference source not found.**

Table 7-28. Analysis Visit Windows for PD Plasma Biomarker Assessments Based on Core Study Day^a

| Analysis Visit | Target Day | T-T Analysis Visit Window | P-TC Analysis Visit Window ^b |
|----------------|------------|---------------------------|---|
| Core Baseline | 1 | ≤ 1 | ≤ 1 |
| Week 1 | 8 | [2, 12] | [2, 12] |
| Week 2 | 15 | [13, 22] | [13, 22] |
| Week 4 | 29 | [23, 36] | [23, 36] |
| Week 6 | 43 | [37, 50] | [37, 50] |
| Week 8 | 57 | [51, 71] | [51, 71] |
| Week 12 | 85 | [72, 99] | [72, 99] |
| Week 16 | 113 | [100, 141] | [100, 141] |
| Week 24 | 169 | [142, 211] | [142, 211] |
| Week 36 | 253 | [212, 295] | [212, 295] |
| Week 48 | 337 | [296, 379] | [296, min (379, LTE Day 1)] |
| Week 60 | 421 | [380, 463] | [380, min (463, LTE Day 1)] |
| Week 72 | 505 | [464, 547] | [464, min (547, LTE Day 1)] |
| Week 84 | 589 | [548, 631] | [548, min (631, LTE Day 1)] |
| Week 96 | 673 | [632, 701] | [632, LTE Day 1] |
| Week 104 | 729 | [702, 743] | LTE Week 4 |
| Week 108 | 757 | [744, 785] | LTE Week 8 |
| Week 116 | 813 | [786, 841] | LTE Week 16 |
| Week 124 | 869 | [842, 911] | LTE Week 24 |
| Week 136 | 953 | [912, 995] | LTE Week 36 |
| Week 148 | 1037 | [996, 1065] | LTE Week 48 |
| Week 156 | 1093 | > 1065 | LTE Week 56 |

^a Target Day and Core Study Day are based on Core Study Day 1.

^b LTE Day 1 represents Core Study Day of first dose date of LTE Study. If no such date, use Core study day of the last visit date among Core visits and LTE screening visit. LTE Weeks are from [Table 7-29](#).

Table 7-29. Analysis Visit Windows for PD Plasma Biomarker Assessments Based on LTE Study Day^a

| Analysis Visit | Target Day | Analysis Visit Window |
|----------------|------------|-----------------------|
| LTE Baseline | 1 | ≤ 1 |
| LTE Week 4 | 29 | [2, 43] |
| LTE Week 8 | 57 | [44, 85] |
| LTE Week 16 | 113 | [86, 141] |
| LTE Week 24 | 169 | [142, 211] |
| LTE Week 36 | 253 | [212, 295] |
| LTE Week 48 | 337 | [296, 365] |
| LTE Week 56 | 393 | > 365 |

^a Target Day and LTE Study Day are based on LTE Study Day 1.

Table 7-30. Analysis Visit Windows for CSF Biomarker Assessments Based on Core Study Day^a

| Analysis Visit | Target Day | T-T Analysis Visit Window | P-TC Analysis Visit Window ^b |
|----------------|------------|---------------------------|---|
| Core Baseline | 1 | ≤ 1 | ≤ 1 |
| Week 6 | 43 | [2, 190] | [2, 190] |
| Week 48 | 337 | [191, 421] | [191, min (421, LTE Day 1)] |
| Week 72 | 505 | [422, 589] | [422, min (589, LTE Day 1)] |
| Week 96 | 673 | [590, 855] | [590, LTE Day 1] |
| Week 148 | 1037 | > 855 | LTE Week 48 |

^a Target Day and Core Study Day are based on Core Study Day 1.

^b LTE Day 1 represents Core Study Day of first dose date of LTE Study. If no such date, use Core study day of the last visit date among Core visits and LTE screening visit. LTE Week 48 window is any day > LTE Day 1.

Table 7-31. Analysis Visit Windows for CSF Biomarker Assessments Based on LTE Study Day^a

| Analysis Visit | Target Day | Analysis Visit Window |
|----------------|------------|-----------------------|
| LTE Baseline | 1 | ≤ 1 |
| LTE Week 48 | 337 | > 1 |

^a Target Day and LTE Study Day are based on LTE Study Day 1.

Table 7-32. Analysis Visit Windows for Amyloid PET Assessments Based on Core Study Day^a

| Analysis Visit | Target Day | T-T Analysis Visit Window | P-TC Analysis Visit Window ^b |
|----------------|------------|---------------------------|---|
| Core Baseline | 1 | ≤ 1 | ≤ 1 |
| Week 48 | 337 | [2, 505] | [2, min (505, LTE Day 1)] |
| Week 96 | 673 | [506, 771] | [506, LTE Day 1] |

| | | | |
|----------|------|------------|-------------|
| Week 124 | 869 | [772, 953] | LTE Week 24 |
| Week 148 | 1037 | > 953 | LTE Week 48 |

^a Target Day and Core Study Day are based on Core Study Day 1.

^b LTE Day 1 represents Core Study Day of first dose date of LTE Study. If no such date, use Core study day of the last visit date among Core visits and LTE screening visit. LTE Weeks are from [Table 7-33](#).

Table 7-33. Analysis Visit Windows for Amyloid PET Assessments Based on LTE Study Day ^a

| Analysis Visit | Target Day | Analysis Visit Window |
|----------------|------------|-----------------------|
| LTE Baseline | 1 | ≤ 1 |
| LTE Week 24 | 169 | [2, 253] |
| LTE Week 48 | 337 | > 253 |

^a Target Day and LTE Study Day are based on LTE Study Day 1.

Table 7-34. Analysis Visit Windows for Tau PET Assessments Based on Core Study Day ^a

| Analysis Visit | Target Day | T-T Analysis Visit Window | P-TC Analysis Visit Window ^b |
|----------------|------------|---------------------------|---|
| Core Baseline | 1 | ≤ 1 | ≤ 1 |
| Week 48 | 337 | [2, 421] | [2, min (421, LTE Day 1)] |
| Week 72 | 505 | [422, 589] | [422, min (589, LTE Day 1)] |
| Week 96 | 673 | [590, 771] | [590, LTE Day 1] |
| Week 124 | 869 | [772, 981] | LTE Week 24 |
| Week 156 | 1093 | > 981 | LTE Week 56 |

^a Target Day and Core Study Day are based on Core Study Day 1.

^b LTE Day 1 represents Core Study Day of first dose date of LTE Study. If no such date, use Core study day of the last visit date among Core visits and LTE screening visit. LTE Weeks are from [Table 7-35](#).

Table 7-35. Analysis Visit Windows for Tau PET Assessments Based on LTE Study Day ^a

| Analysis Visit | Target Day | Analysis Visit Window |
|----------------|------------|-----------------------|
| LTE Baseline | 1 | ≤ 1 |
| LTE Week 24 | 169 | [2, 281] |
| LTE Week 56 | 393 | > 281 |

^a Target Day and LTE Study Day are based on LTE Study Day 1.

Table 7-36. Analysis Visit Windows for Tau PET Assessments, Redefined Baseline ^a (Sensitivity Analysis)^b

| Analysis Visit | Target Day | T-T Analysis Visit Window | P-TC Analysis Visit Window ^c |
|----------------|------------|---|---|
| Baseline_R | 1 | ≤ Day 1 Predose, if it exists. If not, then first day of non-missing result (up to Day 421) | |
| Week_R 48 | 337 | [2, 421] | [2, min (421, LTE Day 1)] |
| Week_R 72 | 505 | [422, 589] | [422, min (589, LTE Day 1)] |
| Week_R 96 | 673 | [590, 771] | [590, LTE Day 1] |

| | | | |
|------------|------|------------|-------------|
| Week_R 124 | 869 | [772, 981] | LTE Week 24 |
| Week_R 156 | 1093 | > 981 | LTE Week 56 |

^a Target Day and Core Study Day are based on Core Study Day 1.

^b Redefined baseline: baseline corresponds to either the pre-dose visit (prior to dosing) in Core Study if the pre-dose Tau PET scan is evaluable, or 1st postdose scan in Core Study if the pre-dose Tau PET scan is missing.

^c LTE Day 1 represents Core Study Day of first dose date of LTE Study. If no such date, use Core study day of the last visit date among Core visits and LTE screening visit. LTE Weeks are from [Table 7-35](#).

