#### **7.11.2. Participant Follow-up for ARIA Events**

Participants with new or worsening radiographic evidence of ARIA on post-baseline MRI scans should be evaluated for neurological signs or symptoms during an unscheduled visit.

Investigators should comprehensively review the BMW for the presence of ARIA or other abnormalities. When ARIA has been detected, follow-up BMWs should be reviewed for radiographic evolution/resolution/stabilization of findings. Investigators suspecting ARIA that has not been detected by the MRI Central Reader should contact the Medical Monitor. For instance, if a local radiologist detects a faint area of vasogenic edema or microhemorrhage, which was not documented in the BMW, the Investigator should contact the Medical Monitor.

If participants are determined to have ARIA related symptoms or signs, the Medical Monitor should be contacted within 48 hours. An evaluation of neurologic signs or symptoms may be assessed during an unscheduled visit.

Participants with asymptomatic ARIA-E should be observed; for participants with mild or moderate symptomatic ARIA-E, the use of oral or IV steroids may be considered (see [Table 8](#) below). In the case of severe symptomatic ARIA-E, it is recommended to hospitalize the participant for close observation and consider the use of IV steroids such as high-dose dexamethasone or a similar agent.

All new cases of ARIA-E and/or new cases of ARIA-H will require unscheduled MRI scans every 4-6 weeks until ARIA-E has resolved and/or until ARIA-H has stabilized without new findings. In addition, the Sponsor may request that additional unscheduled MRIs be performed for the detection and follow-up of ARIA.

An Amyloid PET scan should be requested after the first occurrence of ARIA-E for those participants who have opted in to have longitudinal Amyloid PET performed. An unscheduled LP for CSF analysis and plasma may be requested, if not contraindicated, after any occurrence of ARIA-E and/or ARIA-H.

Participants with MRI evidence of ARIA at any visit will be managed according to the guidelines in [Table 8](#).

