**Table 8: Dosing Guidelines for ARIA (Continued)**

Finding	Asymptomatic/Symptomatic	Action
Serious c ARIA-E or Serious ARIA-H	Asymptomatic	Suspend dosing until resolution of ARIA-E or stabilization of ARIA-H. After resolution (ARIA-E) and/or stabilization (ARIA-H), if participant dosing is restarted, they must receive the same dose they received immediately prior to the ARIA-E/ARIA-H findings. After resuming dosing, 5-10 days before their second post-resumption dose, participants must undergo an unscheduled MRI that must be assessed by the central reader for ARIA-E/H before the next dose is administered. Participants who are undergoing dose titration when the ARIA occurs may continue up-titrating at the second post-resumption dose.
A second occurrence of ARIA-E after full resolution of a prior occurrence of ARIA-E	Asymptomatic or Symptomatic	Permanently discontinue treatment

ARIA=amyloid-related imaging abnormality; ARIA-E=amyloid-related imaging abnormality-edema; ARIA-H=amyloid-related imaging abnormality-hemosiderin deposits; MRI=magnetic resonance imaging.

a Mild includes ‘mild’ and ‘mild+’, as scored on the BMW from the Central Reader.

b Moderate includes ‘moderate-’ and ‘moderate+’, as scored on the BMW from the Central Reader.

c Meets criteria for a SAE.

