6.2.7.1 ARIA-E

6.2.7.1.1 *Event Definition*

An event of ARIA-E is defined as an MRI scan where the Brain MRI Worksheet (BMW) shows the presence of vasogenic edema.

6.2.7.1.2 *Severity Definition*

ARIA-E severity is based on radiographic severity as captured on BMWs.

6.2.7.1.3 *Resolution and Time to Resolution Definition*

- ARIA-E is considered resolved for a participant if all the subsequent MRI scans showed no ARIA-E following the last MRI scan showing ARIA-E.
- Time to resolution is defined as the number of days from the exam date of the first MRI scan showing ARIA-E to the exam date of the earliest MRI showing no ARIA-E after the last one showing ARIA-E. If a participant had a resolved but recurrent ARIA-E after the previous one was resolved, both times to resolution are included.
- If there is existing ARIA-E at LTE Baseline, it is not included as a new occurrence during LTE.

6.2.7.1.4 *Time to First Occurrence and Recurrence Definition*

- Time to the first occurrence is defined as the number of days from the first dose date in the LTE Study to the exam date of the first new MRI scan showing ARIA-E.
- For a participant, if there was an MRI scan showing ARIA-E, followed by a subsequent MRI scan not showing ARIA-E, followed by a subsequent MRI scan again showing ARIA-E, this participant is considered to have a reoccurrence of ARIA-E.

6.2.7.2 **ARIA-H**

For the MRI scans collected in the Core Study, the definitions are specified in the Core Study SAP. Definitions below are for the MRI scans collected in the LTE Study.

6.2.7.2.1 *Event Definition*

For the MRI scans collected in the LTE Study, an event of new ARIA-H is defined as an MRI scan at a post-LTE Baseline visit if the overall ARIA-H radiographic severity is Mild, Moderate or Severe as captured on BMWs.

6.2.7.2.2 *Severity Definition*

For the MRI scans collected in the LTE Study, new ARIA-H overall severity and individual component severity are based on the radiographic severity as captured on BMWs.

6.2.7.2.3 *Time to First Occurrence Definition*

Definition is the same as the time to first occurrence definition for ARIA-E.

6.2.8 **Neurological Examination**

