7.1.1.2 Analysis Visit Window Definitions

In LTE and Integrated Analyses, analysis visit windows based on Core Study Day and LTE Study Day will both be implemented.

7.1.1.2.1 *Safety and Pharmacokinetic Data*

Unless otherwise specified, for safety and PK data, the upper bound of a post-baseline analysis visit (except for “>90 Days Post Last Dose”) is the earlier date of specified upper limit and the last dose date of study drug plus 90 days. All safety and PK data that were collected beyond the last dose date of study drug plus 90 days will be assigned the analysis visit window “>90 Days Post Last Dose”.

Safety and PK data will be summarized based on the analysis visits excluding “>90 Days Post Last Dose” (hereinafter may be referred to as “visit”), when applicable. Safety and PK data with “>90 Days Post Last Dose” analysis visit window will only be listed.

Safety and PK data will be allocated to analysis visits corresponding to the analysis visit window intervals in which they fall in as specified in [Error! Not a valid bookmark self-reference.](#) to [Table 7-25.](#)

For safety data, the analysis visits will be displayed in the format of “Week x”. For Group T-T, “Week x” refers to the analysis visits based on Core Study Day. For the Placebo Data of Group P-TC, as defined in Section 3.2, “Week x” refers to the analysis visits based on Core Study Day; and for the TC Data as defined in Section 3.2, “LTE Week x” based on LTE Study Day will be abbreviated and displayed as “Week x”.

Table 7-1. Analysis Visit Windows for C-SSRS Assessments Based on Core Study Day^a

| Analysis Visit | Target Day | T-T Analysis Visit Window | Placebo Analysis Visit Window ^b |
|----------------|------------|---------------------------|--|
| Core Baseline | 1 | ≤ 1 | ≤ 1 |
| Week 24 | 169 | [2, 253] | [2, 253] |
| Week 48 | 337 | [254, 421] | [254, min (421, LTE Day 1)] |
| Week 72 | 505 | [422, 533] | [422, min (533, LTE Day 1)] |
| Week 80 | 561 | [534, 617] | [534, min (617, LTE Day 1)] |
| Week 96 | 673 | [618, 687] | [618, min (687, LTE Day 1)] |
| Week 100 | 701 | [688,715] | [688, LTE Day 1] |
| Week 104 | 729 | [716, 743] | |
| Week 108 | 757 | [744, 771] | |
| Week 112 | 785 | [772, 799] | |
| Week 116 | 813 | [800, 827] | |
| Week 120 | 841 | [828, 855] | |
| Week 124 | 869 | [856, 883] | |
| Week 128 | 897 | [884, 911] | |

| Analysis Visit | Target Day | T-T Analysis Visit Window | Placebo Analysis Visit Window ^b |

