7.4.8 Magnetic Resonance Imaging (MRI) for ARIA-E and ARIA-H Events

Incidence of the occurrence of ARIA-E within each post-baseline visit will be summarized by radiographic severity for each visit (refer to [Table 7-12](#) and [Table 7-13](#) for analysis visit window definitions) and overall. The same incidence table will be summarized for ARIA-H. In addition to radiographic severity for ARIA-H, individual radiographic severity for microhemorrhages, leptomeningeal hemosiderosis, and macrohemorrhages for the occurrence of ARIA-H will also be summarized by visit and overall.

In the case of multiple values in the baseline analysis visit window, the rules described in the Section [7.1.3.2](#) still apply. In the case of multiple values in a post-baseline analysis visit window, the rules described in the Section [7.1.3.2](#) do not apply to this summary, but the worst-case scenario will be applied as below:

- A participant having a record indicating no ARIA-E and a different record indicating ARIA-E is considered experienced ARIA-E per visit or overall.
- A participant having experienced ARIA-E more than once per visit or overall is counted once in the number of participants with ARIA-E per visit or overall.
- The maximum severity is selected if ARIA-E was observed more than once for a participant per visit or overall post-baseline.

The same rules described above also apply to ARIA-H. In addition, the maximum severity of ARIA-H is selected for a participant per visit or overall post-baseline, and the individual radiographic severity corresponding to the selected ARIA-H will be summarized per visit or overall post-baseline.

APOE genotype, time to the first occurrence, resolution, time to resolution, and reoccurrence will be summarized for participants with ARIA-E. APOE genotype and time to the first occurrence will be summarized for participants with post-baseline ARIA-H.

The number and percentage of participants who had post-baseline ARIA-E but did not have ARIA-H any time post-baseline will be summarized. The number and percentage of participants who had ARIA-H but did not have ARIA-E any time post-baseline will be summarized. Similarly, the number and percentage of participants who had ARIA-H and ARIA-E any time post-baseline will be summarized.

Overall incidence of the occurrence of ARIA-E and ARIA-H will also be summarized by APOE genotype.

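### The SAP does not settle whether MRI scans more than 90 days after the last dose count toward ARIA-E resolution, and its listing rule, applied as written, would drop late resolutions in participants who are not redosed

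*SAP*

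**What the plan says.** - **Listing rule.** SAP 7.1.1.2.1: "All safety and PK data that were collected beyond the last dose date of study drug plus 90 days will be assigned" to a late window, and data in that "analysis visit window will only be listed". The upper-bound sentence of the same section opens with a qualifier: "Unless otherwise specified, for safety and PK data, the upper bound of a post-baseline analysis visit". The sentence on listing carries none.
- **What is reported.** SAP 7.4.8: "APOE genotype, time to the first occurrence, resolution, time to resolution, and reoccurrence will be summarized for participants with ARIA-E". That section sets aside the multiple-record rule of SAP 7.1.3.2 for post-baseline MRI. It does not set aside the 90-day rule.
- **How resolution is defined.** SAP 6.2.7.1.3: "ARIA-E is considered resolved for a participant if all the subsequent MRI scans showed no ARIA-E following the last MRI scan showing ARIA-E". It continues: "Time to resolution is defined as the number of days from the exam date of the first MRI scan showing ARIA-E", with the endpoint also taken from an exam date. Neither definition mentions analysis visits or a 90-day limit.
- **Scope.** SAP 6.2.7 confines those definitions to the LTE Analysis and sends the Integrated Analysis to the Core Study SAP. SAP 7.4.8 places the full set of ARIA summaries in the Integrated Analysis and gives the LTE Analysis only an overall ARIA summary.
- **Follow-up.** Protocol 7.11.2 requires "unscheduled MRI scans every 4-6 weeks until ARIA-E has resolved". Protocol 3.2.5 delays the Early Termination visit after an AE-related discontinuation until the event resolves, and Protocol 7.9 follows unresolved events to resolution or stabilisation. Scans after day 90 are therefore to be expected.

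**The concern.** The 90-day clock starts at the last dose. SAP 3.2 defines that as the latest AL002 administration, so it moves forward when dosing resumes. Under Protocol Table 8, suspended dosing resumes only after ARIA-E has resolved, so in participants who restart, the resolving scan precedes the new last dose and always counts.

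The clock does not move for three groups:

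- participants permanently discontinued, for example for "A second occurrence of ARIA-E after full resolution of a prior occurrence of ARIA-E", for serious symptomatic ARIA-E, or for accompanying severe or symptomatic ARIA-H;
- participants whose dosing is suspended and never restarted;
- participants whose ARIA-E is first seen at the End of Study scan.

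If the listing rule governs the resolution summaries, whether a resolving scan is used depends on whether the participant was redosed. The proportion resolved would be too low in these groups, and time to resolution would be averaged over those who cleared early. Truncation can also err the other way: ARIA-E that is clear before day 90 and recurs afterwards would be shown as resolved.

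**Working it through.** The plan gives no figure to reproduce; the 90 days is a rule. The check has two parts.

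**1. Does the listing rule reach MRI?**

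- SAP 6.2 lists MRI abnormalities among the safety variables.
- SAP 7.1.1.2.1 governs the window tables up to Table 7-25. The MRI windows are Tables 7-12 and 7-13.
- SAP 7.4 points safety analyses to SAP 7.1.1.2.1, and SAP 7.1.1.2 covers both the LTE and the Integrated Analyses.
- SAP 7.4.8 already uses last dose plus 90 days when censoring time to first ARIA-E or ARIA-H.

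Read literally, it does. SAP 6.2.7.1.3, read literally, uses every later scan. The two rules give different tables for the same participant, and the SAP does not say which prevails.

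**2. Where does the cut-off fall relative to detection?**

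Inputs: dosing every 28 days (Protocol 3.2.2); MRI 5 to 10 days before the next dose (Protocol Table 9, footnote g); follow-up scans every 28 to 42 days (Protocol 7.11.2); cut-off at day 90 after the last dose (SAP 7.1.1.2.1).

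- Detection day = 28 − 10 = 18 to 28 − 5 = 23.
- Days left = 90 − 18 = 72 to 90 − 23 = 67, which is 10.3 to 9.6 weeks.
- Last usable scan after detection = floor(days left / interval) × interval.

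| Cadence | Follow-up scan days after last dose | Last usable scan after detection |
|---|---|---|
| 4 weeks | 46–51, 74–79, 102–107 (out) | 8 weeks |
| 5 weeks, detected day 18 | 53, 88, 123 (out) | 10 weeks |
| 5 weeks, detected day 23 | 58, 93 (out) | 5 weeks |
| 6 weeks | 60–65, 102–107 (out) | 6 weeks |

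Over all whole-day intervals from 28 to 42 and detection days 18 to 23, the last usable scan lies 4.9 to 10.3 weeks after detection.

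With the ±5-day visit window applied to the dosing interval (23 to 33 days), detection falls on days 13 to 28 and leaves 77 to 62 days (11.0 to 8.9 weeks). If an unscheduled MRI finds ARIA-E on days 1 to 3, the last usable scan is at 10 to 12 weeks.

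**End of Study.** Protocol 3.2.4 puts this visit 8 weeks (56 days) after the last dose, and SAP Table 7-13 has an MRI window there. The next scan falls on day 56 + 28 = 84 (counted), 56 + 35 = 91 (not counted) or 56 + 42 = 98 (not counted). Any follow-up interval longer than 34 days leaves no usable follow-up scan.

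**The case against.** The strongest reply is that the specific definition controls. Resolution is a participant-level measure built on exam dates, whereas the 90-day rule sits under analysis visit windows and is partly qualified. Where the SAP wants a 90-day limit it writes one: treatment-emergent AEs (6.2.2.1.2), AE denominators (7.4.3), and censoring of time to first ARIA (7.4.8). The resolution definition has none. This is a plausible reading, so a reader who infers that late-clearing ARIA-E **is** counted as unresolved goes further than the text. It does not remove the conflict: the listing sentence is unqualified, SAP 7.4.8 grants no exemption, and SAP 6.2.7.1.3 covers only the LTE Analysis. The Core Study SAP may already deal with late scans for the Integrated Analysis; this cannot be checked.

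Three other stronger readings are tempting but unsupported:

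- **That the loss falls on the worst cases.** Table 8 suspends, and does not permanently stop, radiographically severe ARIA-E that is not serious and symptomatic. It permanently stops any second occurrence, even a mild one. Selection is by redosing, which only partly follows severity.
- **That resolution must occur within 6 to 8 weeks of detection.** Those are the last scans on 6-week and 4-week cadences after a scheduled MRI. The limit itself is 9.6 to 10.3 weeks after detection.
- **That a given percentage would be misclassified.** This needs an assumed duration. With exponential duration from detection, the share still unresolved at t weeks is 2^(−t/median). For assumed medians of 4 to 16 weeks this is 25% to 71% at 8 weeks and 35% to 77% at 6 weeks, too wide a range to serve as an estimate.

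It is also fair that resolution is a descriptive summary, that SAP 7.4.8 lists all MRI findings, and that ARIA is recorded as an AESI with an outcome. The information survives outside the summary tables.

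**Conclusion.** SAP 7.1.1.2.1 and 6.2.7.1.3 are not reconciled. If the listing rule is applied as written, participants who are not redosed after ARIA-E lose any resolving scan beyond day 90, those who resume lose none, and both the proportion resolved and the time to resolution are biased. For a scheduled scan on days 18 to 23, the cut-off falls 67 to 72 days after detection, and the last usable follow-up scan is about 5 to 10 weeks after detection. The number of participants affected cannot be estimated, because the documents give no ARIA-E durations.

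A reader might infer that the titration result is at risk. It is not: the endpoint is incidence and severity, the test in SAP 7.4.8 compares proportions with ARIA, and scheduled on-treatment scans fall well inside the limit. The conclusion assumes that follow-up scans are done as the protocol requires and that the Core Study SAP does not already exempt late scans.

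**What to change.** State in SAP 7.4.8, for both the LTE and Integrated Analyses, and in SAP 6.2.7.1.3, that the last-dose-plus-90-days rule does not apply to resolution and time to resolution of ARIA-E whose onset was within the limit, and that these use all MRI scans to the last available one. Keep the 90-day limit for counting first onsets. Report any recurrence first seen after day 90 separately, with a flag, so that the exemption does not blur the onset rule. Check the Core Study SAP definitions for consistency.

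The cost is one SAP sentence, repeated where needed, and a programming flag. The scans are already required by the protocol and listed under the SAP, so no new data are needed.
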